## 6.1.1 Demographics and other baseline characteristics

Demographics and other baseline characteristics will be presented by means of descriptive statistics (by group and in total). Continuous variables will be presented by means of number of observations (N), minimum (min), median, maximum (max), mean, and standard deviation (std). Discrete variables will be presented by frequency and percentage.

## 6.1.2 Covariates and prognostic variables

No covariates are judged to influence the outcome of the primary or any of the secondary variables.

# 6.1.3 Handling of dropouts and missing data

Patients dropping out from the trial prior to study end will not be replaced. Data totally missing will not be estimated.

#### 6.1.4 Multicenter

This study is a multicenter study. However, there is not a priori reason to suspect that there will be any qualitative differences between the centers regarding any of the efficacy variables or regarding the safety variables. Therefore, the primary statistical analyses will not include center in the model.

In order to harmonize the use and handling of the graft materials and dental implant systems, training will be conducted prior to study start at each center.

## 6.1.5 Subgroup analyses

Subgroup analysis is not planned.

VERSION 1.1 27(33)

## 6.2.2 Secondary objectives

The data collected in the study were expressed as mean ± standard deviation (SD). The Wilcoxon rank sum test will be used for statistical analysis.

# 6.3 Determination of sample size

A sample size of 22 participants per treatment group was selected following power calculations and allowing for 10% patient dropout. A sample size of 20 patients was calculated for the primary outcome variable (horizontal bone changes) with the assumption that the detectable difference would amount to 0.7 mm with a standard deviation of 0.8. The type I error probability was set at 0.05 and the statistical power was set at 80%.

VERSION 1.1 28(33)

# 7 STUDY MANAGEMENT

## 7.1 Monitoring

Before first subject into the study, a representative of Sponsor will visit the investigational study site to:

- Determine the adequacy of the facilities
- Discuss with the investigator(s) (and other personnel involved with the study)
  their responsibilities with regard to protocol adherence, and the
  responsibilities of Sponsor or its representatives. This will be documented in
  a Clinical Study Agreement between Sponsor and the investigator.

During the study, a monitor from Sponsor or a company representing sponsor will have regular contacts with the study site, including visits to:

- Provide information and support to the investigator(s)
- · Confirm that facilities remain acceptable
- Confirm that the investigational team is adhering to the protocol, that data are being accurately recorded in the eCRFs, and that investigational product accountability checks are being performed
- Perform source data verification (a comparison of the data in the eCRFs with the subject's medical records at the hospital or practice, and other records relevant to the study). This will require direct access to all original records for each subject (e.g., clinic charts).

The monitor or another Sponsor representative will be available between visits if the investigator(s) or other staff at the center needs information and advice.

# 7.2 Audits and inspections

Authorized representatives of Sponsor, and an Institutional Review Board (IRB) may visit the center to perform audits or inspections, including source data verification. The purpose of a Sponsor audit or inspection is to systematically and independently examine all study-related activities and documents to determine whether these activities were conducted, and data were recorded, analyzed, and accurately reported according to the protocol, ISO 14155, Good Clinical Practice (GCP), guidelines of the International Conference on Harmonization (ICH), and any applicable regulatory requirements.

# 7.3 Training of staff

The principal investigator will maintain a record of all individuals involved in the study (medical, nursing and other staff). He or she will ensure that appropriate training relevant to the study is given to all of these staff, and that any new information of relevance to the performance of this study is forwarded to the staff involved.

# 7.4 Changes to the protocol

Study procedures will not be changed without the mutual agreement of the principal investigators and Sponsor.

VERSION 1.1 29(33)

If it is necessary for the study protocol to be amended, the amendment and/or a new version of the study protocol (Amended Protocol) must be notified to or approved by each IRB, and if applicable, also the local regulatory authority, before implementation. Local requirements must be followed.

If a protocol amendment requires a change to a particular center's Informed Consent Form, then Sponsor and the center's Ethics Committee must be notified. Approval of the revised Informed Consent Form by Sponsor and by the IRB is required before the revised form is used.

Sponsor will distribute administrative changes, amendments and new versions of the protocol to each principal investigator.

## 7.5 Study agreements

The principal investigator at each center must comply with all the terms, conditions, and obligations of the Clinical Study Agreement for this study. In the event of any inconsistency between this Clinical Study Protocol and the Clinical Study Agreement, the Clinical Study Protocol shall prevail.

# 7.6 Study timetable

Before a subject's enrollment in the study and any study-related procedures are undertaken the following should be fulfilled:

- Signed Clinical Study Protocol and other agreements between Sponsor and the Principal Investigator/Study Site
- · Approval of the study by the IRB

VERSION 1.1 30(33)

# 8.2 Pregnancy

Many physiologic changes can be observed in the pregnant patient and should be considered when planning dental treatment. It has been suggested to avoid elective dental procedures in the 1st and 3rd trimesters due to risk of spontaneous abortions, pre-term births, increased patient discomfort, and increased likelihood of intraoperative complications. The ultimate goal in dental therapy during pregnancy should be to educate the patient on the importance of oral hygiene and plaque control, perform periodontal maintenance therapy and treat emergency situations. All women except for postmenopausal women will require a negative urine human chorionic gonadotropin (HCG) test result prior to inclusion in the study to rule out pregnancy. Postmenopausal is considered when the patient has not had her period for an entire year.

Pregnancy itself is not regarded as an AE/ADE unless there is a suspicion that the medical device under study may have interfered with the effectiveness of a contraceptive medication.

Congenital abnormalities/birth defects and spontaneous miscarriages should be reported as SAEs. Elective abortions without complications should not be handled as AEs/ADEs.

VERSION 1.1 32(33)

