## 3.1.1 Visit 1: Screening

Subjects in need of ridge preservation of a single tooth extraction socket in premolars or molars prior to dental implant surgery that are deemed eligible by meeting inclusion and exclusion criteria will be considered for treatment in this study. Third molars will be excluded as a study site.

Screening process will include evaluation of general dental and systemic health. It will also include a clinical and radiographic assessment of the potential study site and the adjacent teeth. Pre-existing intraoral (periapical) radiograph can be used but must not be older than 6 months. All women except for postmenopausal women will require a negative urine human chorionic gonadotropin (HCG) test result prior to inclusion in the study to rule out pregnancy. Postmenopausal is considered when the patient has not had her period for an entire year. Eligible subjects will immediately be scheduled for Visit 2 provided that they fulfill all inclusion and none of the exclusion criterion.

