# 3.1.3 Visit 3: Extraction Tooth and Socket Ridge Preservation Visit 2 (Enrollment) and Visit 3 (Surgery) may occur on the same day.

Pre-Surgical, Surgical, and Post-Surgical Care (at surgical appointment)

Pre-surgical, surgical and post-surgical care will be given at the discretion of the Investigator and recorded in appropriate sections in the CRF:

- Antibiotics
- Analgesics

VERSION 1.1 9(33)

- Sedation
- Anaesthesia

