# 3.1.9 Visit 9: Re-entry and Dental Implant Placement (5 months ± 14 days)

## Pre-Surgical, Surgical, and Post-Surgical Care

See Section 3.1.3.

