#### Pre-Surgical Procedures

Buccal and occlusal photographs of the surgical site will be obtained. Standardized periapical radiograph of a target tooth will be taken.

VERSION 1.1 11(33)

If the bucco-lingual ridge width is judged not enough for implant placement the subject will be terminated from the study and will receive an appropriate treatment and followed according to the clinic's routines.

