#### Surgical Procedure

Implant placement is made per standard procedure. For patients in each treatment group, a trephine drill will be used to harvest a core of bone for descriptive histology. A trephine drill will be used to harvest a core of bone corresponding with the planned implant length. A trephine drill of 2.8 mm in diameter will be used as the first choice. If another diameter has to be used a diameter of the trephine will be recorded in CRF. A length of a trephine will be up to 8 mm. Following harvesting, the trephined bone core will immediately be transferred to a solution of 10% neutral buffered formalin (NBF). These samples are to be used for histomorphometric assessment. Bone Density Classification (Misch Classification)(10) will be evaluated and recorded in CRF.

Selection of implant system will be left to the judgment of study sites; however the same system should be used in all the cases treated at the site. Implant site preparation and placement will proceed according to the implant system manufacturer recommendations.

When one-stage approach is chosen, a healing abutment will be placed to finger tightness. Depending on the buccal soft tissue thickness, the crestal tissue will either be removed or deepithelialized and inverted to the buccal to increase the soft tissue thickness. When two-stage procedure is chosen, a cover screw will be placed and stay buried and left to heal. Once healed, a second surgery is performed to attach an abutment for securing the crown in place. Selection of approach will be left up to the dentist's discretion.

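### Minor safety point: the only required pregnancy test is before inclusion, so it is at least about 19.7 weeks old at the Visit 9 implant surgery, and no repeat is required

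*Combined protocol and SAP*

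**What the plan says.** Section 3.1.1 (Visit 1: Screening) states that women other than postmenopausal women "will require a negative urine human chorionic gonadotropin (HCG) test result prior to inclusion in the study to rule out pregnancy". Section 8.2 repeats the requirement, and exclusion criterion 12 in section 3.2.3 makes a positive result a bar to entry. These are the only mentions of the test.

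Section 8.2 also gives the reasoning. It says "It has been suggested to avoid elective dental procedures in the 1st and 3rd trimesters", naming miscarriage and pre-term birth among the risks. It describes the aim of dental care in pregnancy as teaching oral hygiene, and to "perform periodontal maintenance therapy and treat emergency situations".

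Section 3.1.9 schedules Visit 9 as "Re-entry and Dental Implant Placement (5 months ± 14 days". The pre-surgical steps there are photographs, a periapical radiograph and a judgement of ridge width: "If the bucco-lingual ridge width is judged not enough for implant placement the subject will be terminated from the study". Subjects with enough width go on to implant placement, and "a trephine drill will be used to harvest a core of bone for descriptive histology". For peri-surgical care, Visit 9 refers back to section 3.1.3, which says "Pre-surgical, surgical and post-surgical care will be given at the discretion of the Investigator" and lists antibiotics, analgesics, sedation and anaesthesia. Neither section mentions a pregnancy test, and Table 1 has no row for one.

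**The concern.** The test before inclusion protects the first operation, the extraction and ridge preservation. The second operation is also planned rather than urgent. It involves drilling, an implant and a core taken for histology, with any sedation left to the surgeon. A woman who conceives after entry and does not yet know it could go into that operation with only a result from months before.

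The protocol foresees that pregnancies may occur, since section 4.3.1.2 says how to report them. It does not say how to detect one before the second surgery or what to do with the surgery if one is found. The inclusion criteria and the restrictions in section 3.2.4 contain no contraception rule that could stand in for a repeat test. What is at stake is the safety of very few participants, not the efficacy result.

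**Working it through.** The documents give no figure for the age of the test at Visit 9, so there is none to reproduce.

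**Age of the test at Visit 9**

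- Visit 9 is 5 months ± 14 days after ridge preservation (section 3.1.9). 5 × 365.25 / 12 = 152 days, or 21.7 weeks.
- Shortest gap from test to first surgery: 0 days. Screening and enrollment may share a day (section 3.1.2), and "Visit 2 (Enrollment) and Visit 3 (Surgery) may occur on the same day" (section 3.1.3).
- Longer gap: 14 days. This is an assumption. It reads the partly legible Visit 2 window in Table 1 as up to two weeks before surgery, and takes the test to fall within it.
- Minimum age: 0 + 152 − 14 = 138 days = 19.7 weeks.
- Age with the assumed 14-day gap and the latest Visit 9: 14 + 152 + 14 = 180 days = 25.7 weeks.
- With 30-day months the two figures are 19.4 and 25.4 weeks.

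The minimum follows from the visit schedule. The upper figure is not a limit: the test is described under Visit 1, which has no window in Table 1, so an early screening test could be older.

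**Expected yield of a repeat test**

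No input here is in the documents; all are assumptions.

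- Women who are not postmenopausal among the 44 subjects: 5 to 15.
- Proportion conceiving over about 22 weeks: 1% to 5%.
- Share of those conceptions that are in the first trimester and detectable at Visit 9: 9/22. This dates pregnancy from the last period and leaves out the first 2 weeks, which urine HCG would miss.
- Proportion unrecognised: 25% to 50%.

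Yield = women × conception proportion × 9/22 × proportion unrecognised.

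- Low: 5 × 0.01 × 9/22 × 0.25 = 0.005.
- High: 15 × 0.05 × 9/22 × 0.50 = 0.15.

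A 12-week window in place of 9 gives 15 × 0.05 × 12/22 × 0.50 = 0.20, but that counts pregnancies too early for the test to find.

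**Effect on the primary analysis**

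The primary outcome uses the CBCT at Visit 8, at 4 months ± 7 days. The latest Visit 8 is 4 × 365.25 / 12 + 7 = 129 days; the earliest Visit 9 is day 138. Within the visit windows, the primary data are complete before the repeat test would be done.

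**The case against.** The strongest reply is that this is clinical practice and need not be written into the protocol. The implant is the subject's planned treatment, placed by the usual procedure, with peri-surgical care at the investigator's discretion. Section 8.2 tells investigators to bear pregnancy in mind when planning treatment. An investigator may test, and once a pregnancy is known, the safety clause in section 3.2.5 or exclusion criterion 12 can stop the surgery. This is fair, but all of it works on a known pregnancy. The open question about health problems at each visit (section 4.3.1.2) might prompt a test if symptoms are reported, but it is not designed to find an early pregnancy. Detection is the gap.

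Other parts of the reply stand and limit the point:

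- The yield is far below one subject and rests wholly on assumptions. It starts from 44 subjects although some will drop out or lack ridge width before Visit 9.
- A reader might infer that the protocol breaks a rule of its own. It does not: section 8.2 reports a suggestion, cites no source for it, and does not itself call the implant surgery elective. That label is a reasonable reading of planned tooth replacement.
- The suggestion names the 1st and 3rd trimesters. A pregnancy begun soon after entry could be in the second by Visit 9. The description of care in section 8.2 covers pregnancy as a whole, but the yield above counts first-trimester cases only.
- The Visit 8 CBCT is also a study procedure after entry without a repeat test. The reasons in section 8.2 concern dental procedures, so this point is confined to the surgery.

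**Conclusion.** The point holds as a minor safety improvement. One test is required, before inclusion; it is at least about 19.7 weeks old at the second surgery; nothing requires a repeat. The figure of about 25.7 weeks depends on the assumed two-week window. A reader might take 20 to 26 weeks as the range the protocol fixes, but it fixes only the lower end.

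The size is about 0.005 to 0.15 detectable, unrecognised first-trimester pregnancies in the whole trial. A reader might also infer that the trial's conclusions are at risk. The documents do not support that: the primary measurement comes before Visit 9. The case for the change is that it is cheap and brings Visit 9 into line with the reasoning of section 8.2.

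**What to change.** Add to section 3.1.9, with a row in Table 1, a repeat urine HCG test for women who are not postmenopausal, done at Visit 9 before the pre-surgical radiograph and the surgery. If it is positive, take no bone core and place no implant at that visit, and time the later implant treatment by clinical judgement in line with section 8.2.

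Two further statements are needed:

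- A pregnancy begun after enrollment does not trigger the exclusion in section 3.2.5 (procedures for incorrectly enrolled subjects). That text removes from the analyses anyone who ceases to meet the criteria after enrollment; read with criterion 12, it could discard a valid Visit 8 CBCT. The scan should stay in the primary analysis.
- A core taken outside the ±14-day window is left out of the histology comparison. New bone and residual graft depend on healing time, so a late core is not comparable with one taken at 5 months.

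The cost is one urine test per woman concerned (5 to 15 on the assumed numbers), one table row and a few sentences. Rarely, one subject will have no usable core, and a late or missing re-entry radiograph and later follow-up. No primary-outcome data are lost.
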